5.11 Duration of Follow Up

All patients will be followed for 30 days after the last dose of study treatment or until all treatment-related, clinically significant toxicities resolve to baseline or grade ≤ 1 . Adverse events with attribution of possible, probable, or definite will be reported following guidelines for adverse event reporting, and all SAEs will be reported for 30 days after the last dose of study treatment.

Patients on active treatment at 12 months may continue to receive pembrolizumab but will revert to SOC management and be labeled in “follow-up”. At this time only PFS and long-term toxicity data will be collected every 3 months as part of routine SOC management.

All patients will be followed every 3 months per routine SOC management until documented progression, death, loss to follow up, consent withdrawal, or study termination. Patients who discontinue study treatment early will be followed for progression free survival and late toxicity assessment every 3 months as part of their routine SOC management.

6.0 STUDY ASSESSMENTS AND MONITORING

The study calendar lists all the study assessments and their scheduled times. All data obtained from these assessments will be recorded in the study specific case report forms that will be generated prior to study activation. See Appendix 2 for data submission schedule.

6.1 Study Calendar

Assessment Window (Days)	Screening		Treatment Cycles					End of Treatment	Post-Treatment		
	Days -28 to -1	Cycle 1 (±7days)	Cycle 2			Cycle 3 ^j (±7 days)	Subsequent Cycles (±7 days)				
			Wk 1 (±7days)	Wk 2	Wk 3						
Administrative Procedures											
Inclusion/exclusion criteria	X										
Demographics and Medical History	X										
Prior and concomitant medication review	X	X				X	X				
Survival status							X	X ^c	X		
Clinical Procedures/Assessments											
Physical examination ^a	X	X	X	X	X	X	X		X		
ECOG performance status	X	X	X			X	X				
Vital signs and weight	X	X	X			X	X				
CBC with differential ^b	X	X	X			X	X ^b				
Serum chemistry ^b	X	X	X			X	X ^b				
TSH, free T3, free T4	X	X	X			X	X ^b				
Coagulation panel (PT/INR and aPTT)	X										
Urine pregnancy test	X (within 4d of cycle 1)										
Stool Sample		X ^l									
Review adverse events	X	X	X	X	X	X	X				
Investigational Treatment											
Pembrolizumab ^d		X	X			X	X		X		
Intralesional IL-2 ^e				X	X						
Radiation Therapy ^f			X	X							
Efficacy measurements											
Tumor imaging ^g	X					X	X ^g				
Efficacy ^c							X				

Correlatives/ Biopsy									
Blood samples for immune assays ^h		X ^k	X ^k		X	X	X ^k		
Archival/screening FFPE tumor tissue specimen or 10 unstained slides ^h		X							
Biopsy ⁱ		X			X				

Abbreviations: ECOG=Eastern Cooperative Oncology Group; TSH=Thyroid Stimulating Hormone; T3=Triiodothyronine; T4=Thyroxine; FFPE=Formalin-fixed, paraffin-embedded; CT=Computerized tomography; MRI=magnetic resonance imaging; PFS=progression free survival; SOC=standard of care.

- a. Patients will be clinically evaluated prior to each cycle of pembrolizumab for the first 3 cycles and with each intralesional IL-2 injection, and thereafter every 3 cycles until off treatment.
- b. CBC and serum chemistry, TSH, free T3, free T4 will be obtained 4 days prior to every cycle of pembrolizumab.
- c. ORR, DCR, and PFS will be assessed every 3 cycles using RECIST 1.1 and irRECIST. Patients who complete study treatment, or discontinue study treatment early, will be followed for PFS every 3 months.
- d. Pembrolizumab: q 3 weeks +/- 3 days (one cycle) until intolerable toxicity or progression.
- e. Intralesional IL-2: 4 injections (2 injections per week during Cycle 2 with each injection \geq 48 hours apart), starting 24-96 hours after completion of radiotherapy.
- f. Radiotherapy: 3 fractions of 8 Gy delivered 12-96 hours apart with Cycle 2 of pembrolizumab.
- g. CT or MRI at pre-treatment and q 3 cycles until progression (e.g., at the end of cycle 3, ,6, 9, etc.).
- h. See the correlative study section for detailed information (Section 8.0)
- i. Biopsy: Tumor biopsies will be obtained prior to cycle 1 treatment and during the final intralesional needle placement for IL-2 delivery (Cycle 2 Week 3).
- j. Follow-up: patients on active treatment at 12 months may continue to receive pembrolizumab, but will revert to SOC management and be labeled in "follow-up". At this time only PFS and long-term toxicity data will be collected every 3 months as part of routine SOC management.
- k. Research blood to be drawn prior to starting therapy for cycle 1 and 2. After Cycle 3 research blood to be drawn at cycle 6 then every 6 cycles thereafter.
- l. Stool sample will be collected from patients before initiation of treatment

7.0 TRIAL PROCEDURES

7.1 Response Assessment

7.1.1 Efficacy

Response will be evaluated in this study using the new international criteria proposed by the revised Response Evaluation Criteria in Solid Tumors (RECIST) guideline (version 1.1) [58] as well as irRECIST criteria. Progression will be evaluated using irRECIST criteria. Additionally, imaging will be reviewed by a radiologist in conjunction with a radiation oncologist to help distinguish tumor progression from post-SAR scarring. Changes in the largest diameter (unidimensional measurement) of the tumor lesions and the shortest diameter in the case of malignant lymph nodes are used in the RECIST criteria.

7.1.2 Disease Parameters

7.1.2.1 Measurable Disease

The presence of at least one measurable lesion.

7.1.2.2 Measurable Lesions

Lesions that can be accurately measured in at least one dimension with longest diameter (LD) 20mm using conventional techniques or 10mm with spiral CT scan.

7.1.2.3 Non-Measurable Lesions

All other lesions, including small lesions (longest diameter <20 mm with conventional techniques or <10 mm with spiral CT scan), i.e., bone lesions, leptomeningeal disease, ascites, pleural/pericardial effusion, inflammatory breast disease, lymphangitis cutis/pulmonis, cystic lesions, and also abdominal masses that are not confirmed and followed by imaging techniques.

All measurements should be taken and recorded in metric notation, using a ruler or calipers. All baseline evaluations should be performed as closely as possible to the beginning of treatment and never more than 4 weeks before the beginning of the treatment.

The same method of assessment and the same technique should be used to characterize each identified and reported lesion at baseline and during follow up.

Clinical lesions will only be considered measurable when they are superficial (e.g., skin nodules and palpable lymph nodes). For the case of skin lesions, documentation by color photography, including a ruler to estimate the size of the lesion, is recommended.

7.1.3 Methods of Measurement

CT and MRI are the best currently available and reproducible methods to measure target lesions selected for response assessment. Conventional CT and MRI should be performed with cuts of 10 mm or less in slice thickness contiguously. Spiral CT should be performed using a 5 mm

contiguous reconstruction algorithm. This applies to tumors of the chest, abdomen and pelvis. Head and neck tumors and those of extremities usually require specific protocols.

Lesions on chest X-ray are acceptable as measurable lesions when they are clearly defined and surrounded by aerated lung. However, CT is preferable.

When the primary endpoint of the study is objective response evaluation, ultrasound (US) should not be used to measure tumor lesions. It is, however, a possible alternative to clinical measurements of superficial palpable lymph nodes, subcutaneous lesions and thyroid nodules. US might also be useful to confirm the complete disappearance of superficial lesions usually assessed by clinical examination.

The utilization of endoscopy and laparoscopy for objective tumor evaluation has not yet been fully and widely validated. Their uses in this specific context require sophisticated equipment and a high level of expertise that may only be available in some centers. Therefore, the utilization of such techniques for objective tumor response should be restricted to validation purposes in specialized centers. However, such techniques can be useful in confirming complete pathological response when biopsies are obtained.

Cytology and histology can be used to differentiate between PR and CR in rare cases (e.g., after treatment to differentiate between residual benign lesions and residual malignant lesions in tumor types such as germ cell tumors).

7.1.4 Response Criteria

7.1.4.1 Evaluation of Target Lesions

- **Complete Response (CR):** Disappearance of the target lesion
- **Partial Response (PR):** At least a 30% decrease in the sum of the LD of target lesions, taking as reference the baseline sum LD
- **Progressive Disease (PD):** At least a 20% increase in the sum of the LD of target lesion, or the appearance of one or more new lesions
- **Stable Disease (SD):** Neither sufficient shrinkage to qualify for PR nor sufficient increase to qualify for PD, taking as reference the smallest sum LD since the treatment started

7.1.4.2 Immune Related Response Criteria (irRECIST)

A growing body of literature indicates that radiographic responses to immunotherapy may have different patterns and kinetics than what would be expected with traditional cytotoxic therapies. To account for these differences we will also characterize radiographic outcomes using the immune related response criteria outlined by Wolchok and colleagues [59]. See Appendix 4.

7.1.4.3 Evaluation of Best Overall Response

The best overall response is the best response recorded from the start of the treatment until disease progression/recurrence (taking as reference for PD the smallest measurements recorded

since the treatment started). In general, the patient's best response assignment will depend on the achievement of both measurement and confirmation criteria.

Table 12. Best Overall Response Evaluation

Target Lesion	New Lesion	Overall Response
CR	No	CR
PR	No	PR
SD	No	SD
PD	Yes or No	PD

Patients with a global deterioration of health status requiring discontinuation of treatment without objective evidence of disease progression at that time should be classified as having "symptomatic deterioration". Every effort should be made to document the objective progression even after discontinuation of treatment.

In some circumstances it may be difficult to distinguish residual disease from normal tissue.

When the evaluation of complete response depends on this determination, it is recommended that the residual lesion be investigated (fine needle aspirate/biopsy) to confirm the complete response status.

Duration of Overall Response

The duration of overall response is measured from the time measurement criteria are met for CR or PR (whichever status is recorded first) until the first date that recurrence or PD is objectively documented, taking as reference for PD the smallest measurements recorded since the treatment started.

Duration of Stable Disease

SD is measured from the start of the treatment until the criteria for disease progression are met, taking as reference the smallest measurements recorded since the treatment started.

The clinical relevance of the duration of SD varies for different tumor types and grades.

Therefore, it is highly recommended that the protocol specify the minimal time interval required between two measurements for determination of SD. This time interval should take into account the expected clinical benefit that such a status may bring to the population under study.

Disease Control Rate (DCR)

DCR is defined as the percentage of patients that achieve an objective tumor response or stable disease to therapy.

Progression-Free Survival (PFS)

PFS is defined as the duration of time from start of treatment to time of progression or death, whichever occurs first.

Abscopal Response Rate (ARR)

ARR is defined as the percentage of patients that achieve an objective tumor response at unirradiated lesions as defined by irRECIST criteria.

Reporting of Results

All patients included in the study must be assessed for response to treatment, even if there are major protocol treatment deviations or if they are ineligible. Each patient will be assigned one of the following categories: 1) complete response, 2) partial response, 3) stable disease, 4) progressive disease, 5) early death from malignant disease, 6) early death from toxicity, 7) early death because of other cause, or 9) unknown (not assessable, insufficient data).

All of the patients who met the eligibility criteria should be included in the main analysis of the response rate. Patients in response categories 4-9 should be considered as failing to respond to treatment (disease progression). Thus, an incorrect treatment schedule or drug administration does not result in exclusion from the analysis of the response rate. Precise definitions for categories 4-9 will be protocol specific.

All conclusions should be based on all eligible patients. Subanalyses may then be performed on the basis of a subset of patients, excluding those for whom major protocol deviations have been identified (e.g., early death due to other reasons, early discontinuation of treatment, major protocol violations, etc.). However, these subanalyses may not serve as the basis for drawing conclusions concerning treatment efficacy, and the reasons for excluding patients from the analysis should be clearly reported.

The 95% confidence intervals should be provided.

7.2 Trial Procedures

The Study Calendar - Section 6.0 summarizes the trial procedures to be performed at each visit. Individual trial procedures are described in detail below. It may be necessary to perform these procedures at unscheduled time points if deemed clinically necessary by the investigator.

Furthermore, additional evaluations/testing may be deemed necessary by the Sponsor and/or Merck for reasons related to subject safety. In some cases, such evaluation/testing may be potentially sensitive in nature (e.g., HIV, Hepatitis C, etc.), and thus local regulations may require that additional informed consent be obtained from the subject. In these cases, such evaluations/testing will be performed in accordance with those regulations.

7.2.1 Administrative Procedures

7.2.1.1 Informed Consent

The Investigator must obtain documented consent from each potential subject prior to participating in a clinical trial.

7.2.1.2 General Informed Consent

Consent must be documented by the subject's dated signature or by the subject's legally acceptable representative's dated signature on a consent form along with the dated signature of the person conducting the consent discussion.

A copy of the signed and dated consent form should be given to the subject before participation in the trial.

The initial informed consent form, any subsequent revised written informed consent form and any written information provided to the subject must receive the IRB/ERC's approval/favorable opinion in advance of use. The subject or his/her legally acceptable representative should be informed in a timely manner if new information becomes available that may be relevant to the subject's willingness to continue participation in the trial. The communication of this information will be provided and documented via a revised consent form or addendum to the original consent form that captures the subject's dated signature or by the subject's legally acceptable representative's dated signature.

Specifics about a trial and the trial population will be added to the consent form template at the protocol level.

The informed consent will adhere to IRB/ERC requirements, applicable laws and regulations and Sponsor requirements.

7.2.1.3 Inclusion/Exclusion Criteria

All inclusion and exclusion criteria will be reviewed by the investigator or qualified designee to ensure that the subject qualifies for the trial.

7.2.1.4 Medical History

A medical history will be obtained by the investigator or qualified designee. Medical history will include all active conditions, and any condition diagnosed within the prior 10 years that are considered to be clinically significant by the Investigator. Details regarding the disease for which the subject has enrolled in this study will be recorded separately and not listed as medical history.

7.2.1.5 Prior and Concomitant Medications Review

7.2.1.5.1 Prior Medications

The investigator or qualified designee will review prior medication use, including any protocol-specified washout requirement, and record prior medication taken by the subject within 28 days before starting the trial. Treatment for the disease for which the subject has enrolled in this study will be recorded separately and not listed as a prior medication.

7.2.1.5.2 Concomitant Medications

The investigator or qualified designee will record medication, if any, taken by the subject during the trial. All medications related to reportable SAEs and ECIs should be recorded as defined in Section 7.3.

7.2.1.6 Prior Treatment Details

The investigator or qualified designee will review all prior cancer treatments including systemic treatments, radiation, and surgeries.

7.2.1.6.1 Subsequent Anti-Cancer Therapy Status

The investigator or qualified designee will review all new anti-neoplastic therapy initiated after the last dose of trial treatment. If a subject initiates a new anti-cancer therapy within 30 days after the last dose of trial treatment, the 30-day Safety Follow-up visit must occur before the first dose of the new therapy. Once new anti-cancer therapy has been initiated the subject will move into survival follow-up.

7.2.2 Clinical Procedures/Assessments

7.2.2.1 Adverse Event (AE) Monitoring

The investigator or qualified designee will assess each subject to evaluate for potential new or worsening AEs as specified in the Trial Flow Chart and more frequently if clinically indicated. Adverse experiences will be graded and recorded throughout the study and during the follow-up period according to NCI CTCAE Version 4.0 (see Appendix 5). Toxicities will be characterized in terms regarding seriousness, causality, toxicity grading, and action taken with regard to trial treatment.

Please refer to section 7.3 for detailed information regarding the assessment and recording of AEs.

7.2.2.2 Full Physical Exam

The investigator or qualified designee will perform a complete physical exam during the screening period. Clinically significant abnormal findings should be recorded as medical history. A full physical exam should be performed during screening.

7.2.2.3 Directed Physical Exam

For cycles that do not require a full physical exam per the Trial Flow Chart, the investigator or qualified designee will perform a directed physical exam as clinically indicated prior to trial treatment administration.

7.2.2.4 Vital Signs

The investigator or qualified designee will take vital signs at screening, prior to the administration of each dose of trial treatment and at treatment discontinuation as specified in the Trial Flow Chart (Section 6.0). Vital signs should include temperature, pulse, respiratory rate, weight, and blood pressure. Height will be measured at screening only.

7.2.2.5 Eastern Cooperative Oncology Group (ECOG) Performance Scale

The investigator or qualified designee will assess ECOG status (see Appendix 1) at screening, prior to the administration of each dose of trial treatment and discontinuation of trial treatment as specified in the Trial Flow Chart.

7.2.3 Laboratory Procedures/Assessments

Details regarding specific laboratory procedures/assessments to be performed in this trial are provided below. Laboratory tests for hematology, chemistry, urinalysis, and others are specified in Table 13.

Table 13. Laboratory Tests

Hematology	Chemistry	Urinalysis	Other
Hematocrit	Albumin		Serum β -human chorionic gonadotropin†
Hemoglobin	Alkaline phosphatase		(β -hCG)†
Platelet count	Alanine aminotransferase (ALT)		PT (INR)
WBC (total and differential)	Aspartate aminotransferase (AST)		aPTT
Red Blood Cell Count	Lactate dehydrogenase (LDH)		Total triiodothyronine (T3)
Absolute Neutrophil Count	Carbon Dioxide ‡		Free tyroxine (T4)
Absolute Lymphocyte Count	(CO_2 or bicarbonate)	Urine pregnancy test †	Thyroid stimulating hormone (TSH)
	Uric Acid		
	Calcium		
	Chloride		Blood for correlative studies
	Glucose		
	Phosphorus		
	Potassium		
	Sodium		
	Magnesium		
	Total Bilirubin		
	Direct Bilirubin (If total bilirubin is elevated above the upper limit of normal)		
	Total protein		
	Blood Urea Nitrogen		

† Perform on women of childbearing potential only. If urine pregnancy results cannot be confirmed as negative, a serum pregnancy test will be required.

‡ If considered standard of care in your region.

Laboratory tests for screening or entry into the Second Course Phase should be performed within 10 days prior to the first dose of treatment. After Cycle 1, pre-dose laboratory procedures can be conducted up to 4 days prior to dosing. Results must be reviewed by the investigator or qualified designee and found to be acceptable prior to each dose of trial treatment.

7.2.4 Other Procedures

7.2.4.1 Withdrawal/Discontinuation

When a subject discontinues/withdraws prior to trial completion, all applicable activities scheduled for the final trial visit should be performed at the time of discontinuation. Any adverse events that are present at the time of discontinuation/withdrawal should be followed in accordance with the safety requirements outlined in Section 7.3 - Assessing and Recording Adverse Events. Subjects who a) attain a CR or b) complete 12 months of treatment with pembrolizumab may discontinue treatment with the option of restarting treatment if they meet the criteria specified in Section 5.8. After discontinuing treatment following assessment of CR, these subjects should return to the site for a Safety Follow-up Visit (described in Section 5.11) and then proceed to the Follow-Up Period of the study (described in Section 5.11).

7.2.5 Visit Requirements

Visit requirements are outlined in Section 6.0. Specific procedure-related details are provided above.

7.2.5.1 Screening

Screening should be completed within 28 days of Day 1.

7.2.5.2 Treatment period

See study calendar for treatment period details.

7.2.5.3 Post Treatment Visits

7.2.5.3.1 Safety Follow-up Visit

The mandatory Safety Follow-Up Visit should be conducted approximately 30 days after the last dose of trial treatment or before the initiation of a new anti-cancer treatment, whichever comes first. All AEs that occur prior to the Safety Follow-Up Visit should be recorded. Subjects with a treatment related AE of Grade > 1 will be followed until the resolution of the AE to Grade 0-1 or until the beginning of a new anti-neoplastic therapy, whichever occurs first. SAEs that occur within 90 days of the end of treatment or before initiation of a new anti-cancer treatment should also be followed and recorded. Subjects who are eligible for retreatment with pembrolizumab (as described in Section 5.8) may have up to two safety follow-up visits, one after the Treatment Period and one after the Second Course Phase.

7.2.5.4 Follow-up Visits

Subjects who discontinue trial treatment for a reason other than disease progression will move into the Follow-Up Phase and should be assessed every 6 weeks by radiologic imaging to monitor disease status or per standard of care. After 1 year, the imaging time point will occur every 9 weeks or per standard of care. Every effort should be made in the follow up phase to collect information regarding disease status until the start of new anti-neoplastic therapy, disease progression, death, end of the study or if the subject begins retreatment with pembrolizumab as

detailed in Section 5.8. Information regarding post-study anti-neoplastic treatment will be collected if new treatment is initiated.

Subjects who are eligible to receive retreatment with pembrolizumab according to the criteria in Section 5.8 will move from the follow-up phase to the Second Course Phase when they experience disease progression.

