2.0 TRIAL DESIGN

Patients with advanced solid malignancies or lymphoma with progression on prior PD-1/L1 blockade will be enrolled. A total maximum of 25 patients will be enrolled.

Primary Objective: Abscopal response rate, ORR, DCR, PFS
Secondary Objective: Maximum tolerated dose (MTD), safety, and toxicity
Collateral Objectives: Immunophenotype serial tumor biopsies and blood samples

Phase I: IL-2 Dose Findin: 3+3 Design: (3-6 patient dose level, 6-18 patients total)				
	Treatment 1 dose	Treatment 2 dose	Treatment 3 dose	Treatment4 dose
Dose Level -1	1 x 10 ⁶ IU	1 x 10 ⁶ IU	1 x 10 ⁶ IU	1 x 10 ⁶ IU
Dose Level 1	3 x 10 ⁶ IU	3 x 10 ⁶ IU	3 x 10 ⁶ IU	3 x 10 ⁶ IU
Dose Level 2	3 x 10 ⁶ IU	7 x 10 ⁶ IU	7 x 10 ⁶ IU	7 x 10 ⁶ IU
Dose Level 3	3 x 10 ⁶ IU	7 x 10 ⁶ IU	15 x 10 ⁶ IU	15 x 10 ⁶ IU

Phase II: IL-2 Dose Expansion Binomial one-Stage Design (18 additional patients; analyzed with patients from MID)	

 P= 0.05, p1= 0.20, r1= 0, n1= 10, rTot=3, nTot=21, a= 0.1, power=0.8 Response will be assessed according to irRECIST and will be evaluated at the non-treatment lesions (abscopal response) 	

CT= computed tomography, DCR=disease control rate, MTD=maximum tolerated dose, ORR=objective response rate, PFS=progression free survival, RT=radiotherapy, P=pembrolizumab,

- a. Patients will be clinically evaluated prior to each cycle of pembrolizumab for the first 3 cycles and weekly during intralesional IL-2 injections, and thereafter every 3 cycles until off treatment.
- b. Laboratory evaluation will occur pre-treatment at every cycle.
- c. For response assessment, patient will have CT imaging pre-treatment and after every three cycles of pembrolizumab.

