3.0 OBJECTIVES

3.1 Primary Objective

1. To determine if this regimen converts patients with resistance to PD-1/PD-L1 checkpoint blockade into responders as determined by abscopal response rate (defined as response rate at lesions not treated with RT + IL-2) using immune related RECIST (irRECIST)
2. To determine the objective response rate (ORR), disease control rate (DCR), and progression free survival (PFS) using RECIST 1.1 (Response Evaluation Criteria for Solid Tumors)

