Repeat scan shows SD, PR, or CR ⁱ	Continue regularly scheduled imaging assessments every 6 weeks x 3 then resume imaging every 12 weeks thereafter.	Continue study treatment at the investigator's discretion	Continue regularly scheduled imaging assessments every 6 weeks x 3 then resume imaging every 12 weeks thereafter.	May restart study treatment if condition has improved and/or clinically stable per investigator's discretion

ⁱ SD, PR, CR is based on new baseline from first evidence of PD.

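### Tumour-assessment intervals conflict across sections and change with treatment course, so recorded PFS, a listed primary endpoint, depends partly on which schedule a patient is put on

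*Combined protocol and SAP*

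**What the plan says.** PFS is a primary endpoint. Section 2.0 reads "Primary Objective: Abscopal response rate, ORR, DCR, PFS"; Sections 3.1, 5.2 and 8.4 (Table 14) also list it as primary. Section 7.1.4.3 states that "PFS is defined as the duration of time from start of treatment to time of progression or death, whichever occurs first".

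The intervals for assessing progression are:

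- **On treatment (6.1, footnote g):** "CT or MRI at pre-treatment and q 3 cycles until progression". A cycle is 3 weeks, so this is nominally every 9 weeks. Sections 2.0 and 5.2 agree.
- **Stopped for a reason other than progression (7.2.5.4):** patients "should be assessed every 6 weeks by radiologic imaging to monitor disease status or per standard of care", moving to every 9 weeks after 1 year, again with standard of care as the alternative.
- **Stopped early (5.11):** patients "will be followed for progression free survival and late toxicity assessment every 3 months", within routine care. Footnote c of 6.1 gives the same interval for patients who complete treatment or stop early. Patients still on pembrolizumab at 12 months also move to 3-monthly PFS data collection.
- **First progression not confirmed on the repeat scan (5.8.1, Table 11):** "Continue regularly scheduled imaging assessments every 6 weeks x 3 then resume imaging every 12 weeks thereafter".
- **Section 8.1:** places the first response assessment at 6 weeks.

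The criteria also vary. Section 3.1 specifies "disease control rate (DCR), and progression free survival (PFS) using RECIST 1.1", Section 7.1.1 says "Progression will be evaluated using irRECIST criteria", and Table 14 lists both.

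**The concern.** A progression seen on imaging is recorded at the scan that shows it. A longer gap between scans therefore records the same underlying progression later. Here the gap depends on whether the patient is still on treatment, on dose delays if cycles are counted by doses given, and on which section the site follows once treatment stops.

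The analysis plan does not make up for this. Section 7.1.4.3 has no rule for dating progression between scans, for missed scans or for censoring. Section 9.4 plans Kaplan-Meier plots for disease-free survival and does not name PFS. The trial has one arm and at most 25 patients, so a PFS estimate is useful mainly when set beside other data, and that requires a known and uniform assessment interval.

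**Working it through.** **1. Side-by-side reading.**

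| Patient state | Source | Interval |
|---|---|---|
| On treatment | 2.0, 5.2, 6.1 footnote g | 3 cycles × 3 weeks = 9 weeks |
| Stopped, no progression | 7.2.5.4 | 6 weeks, 9 after 1 year, or standard of care |
| Stopped, no progression | 5.11; 6.1 footnote c | 3 months (PFS follow-up) |
| First progression not confirmed | Table 11 | 6 weeks × 3, then 12 weeks |
| First response assessment | 8.1 v 6.1 footnote g | 6 weeks v end of cycle 3 |

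Rows 2 and 3 describe the same patient, and no text says which governs. Table 11 presents its intervals as the regular schedule, but the calendar contains no such schedule. On-treatment scans are tied to cycles. Section 5.4.3 lets pembrolizumab be withheld for toxicity, with up to 12 weeks from the last dose for resolution, and interrupted for other reasons. The documents do not say whether a scan falls due by doses given or by calendar.

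**2. Size.** The documents give no expected PFS median, event count or power for PFS, so there is no stated figure to reproduce. What follows is an illustration.

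- Assumed: exponential time to progression with true median m, F(t) = 1 − 2^(−t/m).
- m = 2.3, 4 and 6 months × 52/12 = 9.97, 17.33 and 26 weeks. The 2.3 months is the background NSCLC figure in Section 4.5.1, from a different population; 4 and 6 months are assumptions.
- 3 months is taken as 13 weeks and read as a scan.
- The patient is scanned at week 9 and then stops treatment without recorded progression.
- Scans are then at 9, 15, 21, 27, … (6-weekly) or 9, 22, 35, … (3-monthly).
- The recorded median is the first scan s with F(s) ≥ 0.5.
- Mean delay = Σ s_j [F(s_j) − F(s_(j−1))] − m/ln 2.

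| True median (weeks) | 6-weekly: F at successive scans → median | 3-monthly: F at successive scans → median | Shift | Mean delay (weeks) |
|---|---|---|---|---|
| 9.97 | F(9) = 0.465, F(15) = 0.648 → 15 | F(9) = 0.465, F(22) = 0.783 → 22 | 7 | 4.0 v 6.3 |
| 17.33 | F(15) = 0.451, F(21) = 0.568 → 21 | F(9) = 0.302, F(22) = 0.585 → 22 | 1 | 3.6 v 6.4 |
| 26 | F(21) = 0.429, F(27) = 0.513 → 27 | F(22) = 0.444, F(35) = 0.607 → 35 | 8 | 3.4 v 6.4 |

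**3. Only a fraction f stops after week 9.** The rest stay on 9-weekly scans. The recorded fraction at t is f × F(last off-treatment scan by t) + (1 − f) × F(last 9-weekly scan by t).

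- f = 5%: 18 v 18, 18 v 18 and 27 v 27 weeks, so no shift.
- f = 20%: 15 v 18, 18 v 22 and 27 v 35 weeks. For m = 26 under 3-monthly follow-up, week 27 gives 0.20 × 0.444 + 0.80 × 0.513 = 0.499, just under one half, so the median moves to week 35.

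The median moves in jumps between scan dates, so its shift does not fall steadily with f. The mean does: the difference in mean delay is about 2.3 to 3.0 weeks if all stop, and 0.20 × that, about 0.5 to 0.6 weeks, if 20% stop. The documents give no rate of early stopping, so f is an assumption. Deaths have exact dates, which reduces all these delays.

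**The case against.** The case for leaving this alone has real content.

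- **The 3-month text does not order a scan.** It speaks of following patients for PFS in routine care, and Section 7.2.5.4 allows standard of care, so the two can be read together. This stands as a reading. It removes the literal clash only by leaving the off-treatment interval open, which does not help the endpoint.
- **Table 11 applies only after a first progression.** Under RECIST 1.1 that progression is already the PFS event, so Table 11 can move only PFS by irRECIST. This stands.
- **PFS has no hypothesis, benchmark or sample size.** The decision rule in Section 9.1 rests on abscopal response, and Section 9.4 calls all results preliminary. This stands and limits the weight of the point.
- **The illustration is coarse.** Having everyone stop at week 9 is an extreme case, and medians snap to scan dates. This also stands, which is why the partial-stopping and mean-delay results are shown.

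A reader might go further and apply each interval to all patients from day 1. With a true median of about 10 weeks, that gives recorded medians of 12, 18 and 13 weeks for 6-, 9- and 13-weekly scans. Those figures are an artefact: no patient is scheduled that way, and at 17.3 weeks the same method gives 18, 18 and 26, a different ranking. A reader might also conclude that PFS becomes uninterpretable. The documents do not support that; what they support is an estimate that is harder to compare with outside data.

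**Conclusion.** The conflict is real and should be corrected. The clearest case is the patient who stops early without progression, for whom Sections 7.2.5.4 and 5.11 (with footnote c) give different intervals. Cycle-linked scanning, Table 11 and Section 8.1 add further mismatches with the calendar. As written, recorded PFS depends partly on treatment course and on the section followed.

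Under the exponential assumption and the three assumed medians, the choice between 6-weekly and 3-monthly assessment moves the recorded median by 1 to 8 weeks if every patient stops after week 9. It has no effect if 5% do. The average effect shrinks in proportion to the share who stop and is reduced further by deaths. The harm is to a descriptive estimate: no between-arm comparison exists to be biased, and the abscopal response decision is unaffected.

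**What to change.** Reconcile 5.8.1 with Table 11, 5.11, 6.1 (footnotes c and g), 7.2.5.4 and 8.1 to one tumour-assessment schedule for PFS. It should be counted in calendar time from the start of treatment, not moved by dose delays, and be the same on and off treatment until progression. The interval is the sponsor's choice, and Table 11's rules on continuing or stopping treatment need not change for this purpose.

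State how progression is dated, and how PFS is censored when scans are missed. Report the actual scan intervals alongside the PFS estimate.

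The cost is amendment wording. Some off-treatment patients may have slightly more or fewer scans than under the section now followed.
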